#### **7.2.3 Pregnancy**

Females must be instructed to stop taking the study medication and immediately inform the investigator if pregnancy occurs during the study. Pregnancies occurring up to 3 months after the completion of the study medication must also

be reported to the investigator. The investigator should report all pregnancies within 24 hours to the sponsor.

The investigator should counsel the patient; discuss the risks of continuing with the pregnancy and the possible effects on the fetus. Monitoring of the patient should continue until conclusion of the pregnancy.

Pregnancy occurring in the partner of a male patient participating in the study should also be reported to the investigator and the sponsor. The partner should be counseled and followed as described above.

## **8. PHARMACEUTICAL INFORMATION**

### **8.1 Regorafenib: description of mechanism of action**

Regorafenib is a small molecule inhibitor of multiple membrane-bound and intracellular kinases involved in normal cellular functions and in pathologic processes such as oncogenesis, tumor angiogenesis, and maintenance of the tumor microenvironment.

### **8.2 Administration of Study Drugs**

Regorafenib or placebo will be administered as monotherapy during the study. The starting dose of regorafenib on study is 160 mg daily for 3 weeks on, 1 week off. The pediatric starting dose is 82 mg/m^2, rounding to the nearest 20 mg, and capping at 160 mg as with adult patients. One cycle is 28 days. Dose reduction levels are noted elsewhere in this protocol document (see Section 6.1.2).

Four 40 mg regorafenib or four placebo tablets should be taken in the morning with approximately 8 fluid ounces (240 mL) of water after a low-fat (< 30% fat) breakfast. Some examples of low fat breakfasts are:

- Two slices of white toast with 1 tablespoon of low-fat margarine and 1 tablespoon of jelly and 8 ounces (240 mL) of skim milk (approximately 319 calories and 8.2 g of fat)
- One cup of cereal, 8 ounces (240 mL) of skim milk, one piece of toast with jam (no butter or marmalade), apple juice, and one cup of coffee or tea (2 g fat, 17 g protein, 93 g of carbohydrate, 520 calories).

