#### **4.3 Treatment assignment**

Eligible patients will be registered by the site personnel and randomized at time of registration by the SARC operations office. For patients on substudies requiring randomization, subjects will be randomly assigned to receive either regorafenib 160 mg once daily or placebo (1:1), 3 weeks on, 1 week off.

Patients, investigators who give the treatment, those assessing outcomes, and those who will perform outcome analyses are blinded as to the allocation. Treatment allocation will remain masked until the time of disease progression, at which time assignment will be unblinded, so that patients on placebo may be crossed over to active treatment.

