### 5.4 Study drug administration

Regorafenib (or placebo) is administered as monotherapy during the study. For adults on the study, the starting dose is 160 mg daily for 3 weeks on, 1 week off, taken in the morning with a low-fat meal each day.

The medication should be taken within 8 hours of the same time each day, otherwise should be marked as a missed dose. One cycle is 28 days.

For adults, four 40 mg regorafenib or placebo tablets should be taken in the morning with approximately 8 fluid ounces (240 mL) of water after a low-fat (< 30% fat) breakfast. Some examples of low-fat breakfasts are:

- Two slices of white toast with 1 tablespoon of low-fat margarine and 1 tablespoon of jelly and 8 ounces (240 mL) of skim milk (approximately 319 calories and 8.2 g of fat).
- One cup of cereal, 8 ounces (240 mL) of skim milk, one piece of toast with jam (no butter or marmalade), apple juice, and one cup of coffee or tea (2 g fat, 17 g protein, 93 g of carbohydrate, 520 calories).

The medication will be taken in a similar fashion in pediatric patients (< 18 years). ... Pediatric patients on trial will receive tablets according to the dosing table below (Table 5.4). The starting dose is 82 mg/m^2 daily with the same 3 week on, 1 week off schedule as for adult patients. The regorafenib dose will be rounded to the nearest 20 mg and capped at 160 mg as with adult patients. The lowest permissible dose is 20 mg. The minimum body surface area to participate is 0.65m^2 and minimum weight is 15 Kg. (33 lbs.)

Table 5.4 – Pediatric Doses

	BSA > 0.65m 
Dose level 0 (standard starting dose)	82 mg/m  oral daily

For dose modifications, for adult and pediatric patients, refer to tables in Section 6 of the protocol.

Patients, or their guardians, should be instructed to record daily regorafenib or placebo dose on the Study Drug diary which will be provided to them (Appendix C).

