## **6. DOSING DELAYS/DOSE MODIFICATIONS**

### **6.1 Dose Reduction Levels**

**In adults, the starting dose of regorafenib is 160 mg once daily for Cohorts C, D and E. The starting dose for Cohorts A and B is 4 tablets of regorafenib or placebo daily.**

**For pediatric patients (< 18 years of age), the starting dose is 82 mg/m^2 (rounding to nearest 20 mg), with a maximum daily dose capped at 160 mg. Please refer to dosing table in Section 5.2.**

Study medication will be administered on a 3-weeks on, 1-week off schedule (3 weeks out of every 4).

Doses will be delayed or reduced for clinically significant hematologic and non-hematologic toxicities that are related to protocol therapy according to the guidelines shown in the Dose Delays/Dose Modifications table that follows. In general, this will mean clinically meaningful G 3 or worse toxicity, although clinically significant G 2 toxicity may qualify, according to the treating physician. Dose modifications will follow predefined dose levels. Dose adjustments for hematologic toxicity are based on the blood counts obtained in preparation for the day of treatment.

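### Section 8.2 gives a BSA-based dose for children, then a four-tablet instruction with no age limit, so it contradicts itself and Section 5.4

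*Combined protocol and SAP*

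**What the plan says.** Two sections carry nearly the same administration instruction, with the same breakfast examples. Section 5.4 limits it by age: "For adults, four 40 mg regorafenib or placebo tablets should be taken in the morning". It then gives the pediatric starting dose of 82 mg/m² and refers to Table 5.4. Section 8.2, in the pharmaceutical chapter, opens with "The starting dose of regorafenib on study is 160 mg daily for 3 weeks on, 1 week off". It next gives 82 mg/m² for pediatric patients with the rounding and the cap, and its following paragraph begins "Four 40 mg regorafenib or four placebo tablets should be taken in the morning". Neither the opening sentence nor the tablet sentence of 8.2 names an age group.

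Two other places give the fixed dose without an age limit, both for the randomized cohorts. Section 4.3 says "subjects will be randomly assigned to receive either regorafenib 160 mg once daily or placebo (1:1), 3 weeks on, 1 week off". Section 6.1 says "The starting dose for Cohorts A and B is 4 tablets of regorafenib or placebo daily". The sentence just before that one in 6.1 is limited to adults: "In adults, the starting dose of regorafenib is 160 mg once daily for Cohorts C, D and E". The paragraph just after it gives the 82 mg/m² dose for patients under 18, then sends the reader to a dosing table in Section 5.2.

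On eligibility, Section 3.1.1 admits patients from age 5 to the rhabdomyosarcoma cohort (D) and from age 10 to the other cohorts. Section 3.1.3 sets a minimum BSA of 0.65 m². Section 5.1 marks accrual as complete for Cohorts A, B and C, but not for D or E.

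**The concern.** Section 8 is where dispensing staff would naturally look for how the drug is given. There, a patient under 18 is covered by two instructions that agree only if 82 mg/m² rounds or caps to 160 mg. For a smaller child they give different amounts. Section 8.2 offers no tablet count for children to set against the count of four.

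This is an operative instruction for a population the trial expects. Section 2.5 says that a substantial majority of embryonal and alveolar rhabdomyosarcoma patients are pediatric. Section 13 requires strict adherence to everything the protocol specifies, so a site should not have to choose between two current statements of how much drug a child takes.

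**Working it through.** The plan states no ratio between the two instructions, so there is no figure of its own to reproduce. The check compares the passages and then sizes the gap.

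**Step 1. Passages side by side.**
- Section 5.4: the four-tablet sentence is limited to adults, and a separate pediatric dose follows.
- Section 8.2: 160 mg with no age limit, then the pediatric dose, then four tablets with no age limit.
- Section 4.3: 160 mg for randomized subjects, with no age limit and no pediatric dose.
- Section 6.1: an adult sentence (Cohorts C, D and E), an unqualified sentence (Cohorts A and B), then a pediatric paragraph. Only the middle sentence is ambiguous.
- Section 5.2: packaging and storage only. The pediatric table that 6.1 places there is Table 5.4.

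**Step 2. Who is affected.** Cohorts D and E are single-arm and not marked as complete, so Section 4.3 and the Cohorts A and B sentence of 6.1 do not concern them. For these cohorts, the unqualified text at issue is in 8.2. Cohort D admits the youngest patients.

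**Step 3. Size of the gap under a literal reading.** Inputs: 82 mg/m², rounding to the nearest 20 mg and a cap of 160 mg (Sections 5.4, 6.1 and 8.2); four 40 mg tablets (8.2); minimum BSA 0.65 m² (3.1.3).

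Tablet instruction: 4 × 40 = 160 mg.
BSA-based dose: 82 × BSA, rounded to the nearest 20 mg, at most 160 mg.
Ratio: 160 / rounded dose.

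| BSA (m²) | 82 × BSA (mg) | Rounded (mg) | Ratio |
|---|---|---|---|
| 0.65 | 53.3 | 60 | 2.67 |
| 0.86 | 70.5 | 80 | 2.00 |
| 1.0 | 82.0 | 80 | 2.00 |
| 1.1 | 90.2 | 100 | 1.60 |
| 1.2 | 98.4 | 100 | 1.60 |
| 1.4 | 114.8 | 120 | 1.33 |
| 1.6 | 131.2 | 140 | 1.14 |
| 1.83 | 150.1 | 160 | 1.00 |

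The rounded dose stays at 60 mg until 82 × BSA reaches 70, that is up to 70/82 = 0.854 m². The ratio of 2.67 therefore holds from 0.65 to about 0.85 m². The rounded dose reaches 160 mg at 150/82 = 1.83 m², and from there the two instructions agree. Without rounding, the ratio at 0.65 m² is 160/53.3 = 3.0.

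**Step 4. Scale against the plan's own pediatric data.** At 0.65 m², 160 mg is 160/0.65 = 246 mg/m². The highest level in the pediatric phase I study described in Section 2.4.3 is 93 mg/m². A dose of 160 mg exceeds that level at any BSA below 160/93 = 1.72 m².

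**The case against.** The strongest reply is that the protocol's intent is clear. The synopsis, Section 5.4, Section 6.1 and Table 6.1.2 all give the BSA-based dose for patients under 18. Section 8.2 gives it too, just before the tablet sentence, and describes the 160 mg cap as shared with adults. It also points to 6.1.2, which matches the number of the pediatric dose-level table. A careful pharmacist meets the pediatric dose first and would probably resolve the conflict. That stands, and it limits how far the point can be taken. It does not remove the contradiction, because the tablet sentence is still an unqualified instruction and its counterpart in 5.4 shows that the qualifier was thought necessary.

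Three stronger readings are tempting, and the documents do not support them.
- A reader might infer that the protocol directs small children to take 160 mg. It does not. No passage says that a child receives 160 mg regardless of BSA.
- A reader might infer that Section 6.1 as a whole sets the adult dose for all ages. It does not. It separates adults from pediatric patients, and only the Cohorts A and B sentence fails to repeat the qualifier.
- A reader might attach the 2.7 ratio to Sections 4.3 and 6.1. Those passages concern cohorts that admitted patients from age 10. The BSA floor of 0.65 m² formally applied there too, but such patients would usually be larger. The documents give no BSA by age. Assuming 1.0 to 1.2 m², the ratio is 2.0 to 1.6. Enrollment to both cohorts is complete in any case.

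**Conclusion.** The point holds as an internal contradiction in current text. Section 8.2 disagrees with itself and with Section 5.4 on what a patient under 18 takes, and the practical weight falls on the cohorts still enrolling, above all Cohort D. Applied literally, the tablet sentence would give from 2.7 times the rounded BSA-based dose at the smallest eligible patients down to parity from about 1.83 m². These ratios rest on the protocol's own rounding rule and on a literal reading. They measure what a misreading could cost and are not a forecast of what sites do. The missing age limits in Section 4.3 and in the Cohorts A and B sentence of Section 6.1 are the same kind of slip with little forward effect. The wrong cross-reference in 6.1 is minor in itself, but it misdirects a reader who is looking for the pediatric table.

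**What to change.** Reconcile Section 8.2 (the opening dose sentence and the tablet sentence), Section 4.3 and the Cohorts A and B sentence of Section 6.1 with Section 5.4 and the pediatric paragraph of Section 6.1, so that all of them state one consistent rule by age. Correct the reference in Section 6.1 to the pediatric dosing table, which is in Section 5.4. Which dose applies to which patients is for the sponsor's medical team to settle, and this review takes no position on it.

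The cost is a few words in three sections and one corrected cross-reference. Until the amendment is in force, a short notice to site pharmacies could flag the conflict and give the sponsor's reading. No change to the design, sample size or analysis is needed.

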### **8.3 Formulation, Packaging and Labelling of Study Drugs**

#### Tablets:

Regorafenib 40 mg tablets contains regorafenib and the inactive excipients microcrystalline cellulose, croscarmellose sodium, magnesium stearate, povidone, colloidal anhydrous silica, polyvinyl alcohol-part hydrolyzed, talk, titanium dioxide E171 (color index 77891), Macrogol/PEG 33350, lecithin (soy), iron oxide yellow – E172 (color index 77491), iron

oxide red – E172.

Where applicable, placebo control tablets without regorafenib will be provided by Bayer.

Regorafenib or placebo tablets will be packaged in high density polyethylene bottles with a white child resistant closure and induction seal. Each bottle includes 30 tablets and a 3 gram desiccant. The bottles will have a label affixed containing study identification, product identification, and quantity of tablets. Once the drug has been received it must be kept in a secure, dry location. Study drugs must be stored in their original bottles at a temperature of 20-25 °C (68-77 °F); provisional temperature limits permitted to 15-30 °C (59-86 °F). The study drugs must be exclusively used for the investigation specified in this protocol and they will only be accessible to authorized staff.

#### **8.4 Agent Ordering**

Regorafenib and placebo tablets for this trial will be provided by Bayer, and distributed by a third party pharmaceutical distribution firm to the individual sites. Details will be provided in the Operations Manual.

#### **8.5 Agent Accountability**

All study drugs will be stored at the investigational site in accordance with Good Clinical Practice (GCP) and Good Manufacturing Practices (GMP) requirements and the instructions given by the clinical supplies department of the Institution and will be inaccessible to unauthorized personnel.

Accountability and patient compliance will be assessed by maintaining adequate drug dispensing and return records.

Accurate records must be kept for each study drug provided by the sponsor. The drug dispensing log must be kept current and contain the following information:

- Documentation of drug shipments received from the sponsor (date received and quantity)
- Disposition of unused study drug not dispensed to patient
- The identification of the patient to whom the study medication was dispensed
- The date(s) and quantity of the study medication dispensed to the patient.

All supplies, including partially used or empty containers must be returned to the treating institution at the end of the study, and destroyed as required by local or institutional regulations (Section 8.7). Copies of the dispensing & inventory logs must be sent to SARC (use the address in Section 8.7).

Patients will also keep a Study Drug diary to indicate their compliance with therapy and adverse events they experience. These diaries will be reviewed and collected at each patient visit.

## 8.6 Destruction of study drugs

All unused and expired supplies of regorafenib and placebo should be destroyed according to institutional policies. A completed “Unused Study Drug Disposition Form Destruction Confirmation” should be sent to SARC by email to:

[[contact]](mailto:[contact]) or [[contact]](mailto:[contact])

OR faxed to: [contact].

## 9. STUDY EVALUATIONS AND STUDY CALENDAR

### 9.1 Screening Studies

The patient must sign the informed consent form before proceeding with screening.

The following procedures will be performed during the screening period (within 14 days of protocol registration):

- History/demographics
- Physical exam
- Vital signs, to include height, weight, WHO performance status
- Concomitant medications, including herbal and other homeopathic remedies
- Hematology: complete blood count, platelet count, differential, PT (INR), PTT
- Serum Chemistry: electrolytes, chloride, bicarbonate, BUN, creatinine, glucose, ALT, AST, total bilirubin, direct bilirubin, alkaline phosphatase, serum albumin, total protein, calcium, magnesium, phosphorus, lipase, amylase
- Urinalysis
- Serum or urine pregnancy test (for women of childbearing potential)
- Baseline radiologic imaging
- The same modalities should be used throughout the study as this baseline, unless allergies or other adverse events intervene)
- Images must be obtained within 28 days of the 1st day of therapy on study
- Baseline tumor measurements from physical exam
- ECG.

The screening period will be up to 14 days prior to study registration. Laboratory baseline evaluations are to be conducted within 14 days prior to study registration. Radiologic imaging must be done within 28 days of the first day of study treatment. For patients for whom there are 14 days or fewer between registration and the start of treatment, the day 1 laboratory data may be omitted.

Study treatment (day 1) should begin no later than 21 days (and within 28 days of baseline images) after patient enrollment into the study.

## 9.2 On Study Evaluation

The following procedures will be performed during the treatment period. Please note that visits may occur  $\pm 2$  days of the scheduled date,  $\pm 3$  days for weeks of bank holidays. Tumor measurements and reimaging may be done  $\pm 7$  days of the anticipated date. Tumor imaging may be performed at other times as clinically indicated. These will be considered non-protocol standard of care scans.

### Cycle 1, Week 1 day 1

- Demographics, interval history
- Concurrent medications
- Physical Exam
- Vitals signs
- Weight
- WHO performance status
- Hematology: complete blood count, platelet count, differential
- Serum Chemistry: electrolytes, chloride, bicarbonate, BUN, creatinine, glucose, ALT, AST, total bilirubin, direct bilirubin, alkaline phosphatase, serum albumin, total protein, calcium, magnesium, phosphorus, lipase, amylase
- For patients for whom there are 14 days or fewer between registration and the start of treatment, the day 1 blood chemistries and hematology may be omitted
- Adverse event evaluation
- Dispense study drug
- Distribute study drug diary, if not already done.

### Cycle 1 Week 1, between days 4-6

A phone call will be made to the patient during this period to review adverse events.

### Cycle 1 Week 2, day 1

- Demographics, interval history
- Concurrent medications
- Physical Exam
- Vitals signs
- Weight
- WHO performance status
- Hematology: complete blood count, platelet count, differential
- Serum Chemistry: electrolytes, chloride, bicarbonate, BUN, creatinine, glucose, ALT, AST, total bilirubin, direct bilirubin, alkaline phosphatase, serum albumin, total protein, calcium, magnesium, phosphorus, lipase, amylase
- Adverse event evaluation.

### **Cycle 1 Week 3, day 1**

- Demographics, interval history
- Concurrent medications
- Physical Exam
- Vitals signs
- Weight
- WHO performance status
- Hematology: complete blood count, platelet count, differential
- Serum Chemistry: electrolytes, chloride, bicarbonate, BUN, creatinine, glucose, ALT, AST, total bilirubin, direct bilirubin, alkaline phosphatase, serum albumin, total protein, calcium, magnesium, phosphorus, lipase, amylase
- Adverse event evaluation.

### **Cycle 1 Week 4**

Off week from treatment.

- The same modalities should be used throughout the study as baseline, unless allergies or other adverse events intervene.

### **Cycle 2 Week 1, day 1 (Week 5 overall)**

- Demographics, interval history
- Concurrent medications
- Physical Exam
- Vitals signs
- Weight
- WHO performance status
- Hematology: complete blood count, platelet count, differential
- Serum Chemistry: electrolytes, chloride, bicarbonate, BUN, creatinine, glucose, ALT, AST, total bilirubin, direct bilirubin, alkaline phosphatase, serum albumin, total protein, calcium, magnesium, phosphorus, lipase, amylase
- Adverse event evaluation
- Dispense study drug
- Distribute study drug diary
- Collect study drug diary for previous cycle.

### **Cycle 2 Week 3, day 1 (Week 7 overall)**

- Demographics, interval history
- Concurrent medications
- Physical Exam
- Vitals signs
- Weight

- WHO performance status
- Hematology: complete blood count, platelet count, differential
- Serum Chemistry: electrolytes, chloride, bicarbonate, BUN, creatinine, glucose, ALT, AST, total bilirubin, direct bilirubin, alkaline phosphatase, serum albumin, total protein, calcium, magnesium, phosphorus, lipase, amylase
- Adverse event evaluation.

## **Week 8**

Off week from treatment.

Imaging studies for comparison to baseline to be conducted this week.

- The same modalities should be used throughout the study as baseline, unless allergies or other adverse events intervene).

## **Cycle 3 Week 1, day 1 (Week 9 overall) and later**

Treatment continues 3 weeks on, 1 week off.

Visits every 2 weeks until end of cycle 4, then every 4 weeks.

- Tumor measurements and imaging every 8 weeks for 32 weeks, then every 12 weeks. Scans may be done  $\pm 7$  days of expected date.

### **At each visit:**

- Demographics, interval history
- Concurrent medications
- Physical Exam
- Vitals signs
- Weight
- WHO performance status
- Hematology: complete blood count, platelet count, differential
- Serum Chemistry: electrolytes, chloride, bicarbonate, BUN, creatinine, glucose, ALT, AST, total bilirubin, direct bilirubin, alkaline phosphatase, serum albumin, total protein, calcium, magnesium, phosphorus, lipase, amylase
- Adverse event evaluation
- Dispense study drug
- Distribute study drug diary
- Collect study drug diary for previous cycle.

## **9.3 Off Study Evaluations**

### **Off study**

- Demographics, interval history

- Concurrent medications
- Physical Exam
- Vitals signs
- Weight
- WHO performance status
- Hematology: complete blood count, platelet count, differential, if not done as part of end of cycle evaluation
- Serum Chemistry: electrolytes, chloride, bicarbonate, BUN, creatinine, glucose, ALT, AST, total bilirubin, direct bilirubin, alkaline phosphatase, serum albumin, total protein, calcium, magnesium, phosphorus, lipase, amylase, if not done as part of end of cycle evaluation
- Serum or urine chemistry pregnancy test (for women of childbearing potential)
- Tumor measurements and imaging, if not done as part of end of cycle evaluation
- Adverse event evaluation
- Collect study drug diary.

